Music can elicit a positive emotional reaction that lessens the fear²¹ and intensity of unpleasant symptoms such as dyspnea and exercise-induced fatigue.^{22,23} These data raise the possibility that diminishing the fear of dyspnea and fatigue may allow patients to tolerate more challenging physical activity and obtain a greater benefit from rehabilitation. Music also can induce entrainment of motor responses such as walking²⁴ (cuing gait to music).²⁵ Sensorimotor coupling can be optimized by embedding sonic enhancements, known as rhythmic auditory stimulation (RAS)²⁶ in an instrumental track²⁷ (**Fig. 1**). Using RAS-enhanced music, we have been able to lengthen the distance walked by patients with COPD and peripheral artery disease (PAD).¹⁹

In this application, we plan to capitalize on both the sensorimotor coupling of gait with the RAS-enhanced music and the mitigating effect of music over exercise-induced dyspnea and fatigue. We reason that patients with COPD enrolled in our home exercise program augmented by patient-tailored, RAS-enhanced music will experience less dyspnea and fatigue allowing for an increase in exercise intensity and duration. Specifically, we propose to compare the efficacy of a 12-week, home-based exercise program augmented by patient-tailored, RAS-enhanced music to a 12-week traditional home-based exercise program in patients with COPD.

In May 2020 we submitted a VA Merit Review project, “Increasing Physical Activity in Patients Recovering from Prolonged Hospitalization for COVID-19 Through a Home-based, Exercise Program Utilizing Rhythmically Enhanced Music”. This study was not funded as a separate project but VA Merit Review suggested and funded an ‘Administrative Project Modification’ to this parent COPD study in which we will include patients recovering from prolonged COVID19 hospitalization. Specifically, we will use our novel RAS-enhanced music exercise program developed for the parent grant in patients recovering from COVID19. The main goal of the modified proposal for COVID19 patients is to compare the efficacy of a 12-week, home-based exercise program augmented by RAS-therapeutic music and strength training to 12-weeks usual care and strength training in patients recovering from COVID 19.

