Physiological factors of interest include: systemic inflammation, quadriceps strength, recruitment and fatigue, quadriceps function and dimension after rehabilitation. Psychological factors include: self-efficacy, anxiety, depression. Clinical factors include: adherence to the 12-week program, adherence to follow-up and number and severity of exacerbations.

COVID Patients

Objective 1. To determine the efficacy of a 12-week, home-based, patient-tailored, RAS-enhanced music exercise program and strength training in improving functional and clinical parameters in patients recovering from COVID19 with a history of an emergency room and/or hospital admission..

Hypotheses: Compared to patients randomized to a home-based, exercise program without music (control group), patients randomized to a home-based, exercise program augmented with RAST-therapeutic enhanced music (experimental group; hereafter referred to as RAST-music group) will demonstrate greater:

1a- increase in 6-minute walking distance (primary hypothesis);

1b- greater increases in rectus femoris dimensions (ultrasound)

1c- greater quadriceps force and endurance (magnetic femoral nerve stimulation; isokinetic strength testing)

1d- increased sense of emotional investment related to the music experience

Objective 2. To determine whether at 12 weeks the RAS-music group will accumulate a greater volume of daily physical activity than the control group. (same as COPD group)

Hypothesis: The RAST-music group will accumulate a greater volume of daily physical activity than the control group. This will be demonstrated by greater physical activity at 12 weeks (actigraphy).

Objective 3. To determine whether 24-weeks after randomization, gains in 6-minute walk distance and perceived functional improvements will be sustained to a greater extent in the RAST-music group

than in the control group (same as COPD group) and whether there is any change in 6-minute walk distance and perceived functional improvements in the control group.

Hypothesis: The RAST-music group will maintain improvements in measured and perceived function at 24 weeks to a greater extent than the control group. (same as COPD)

Objective 4. *To assess impact of physiological and psychological phenotype and clinical factors including those related to music preference and history on responsiveness to rehabilitation achieved with and without concurrent use of RAST music programs (Exploratory objective).*

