The resulting effect of this integrated synergy will be to promote greater functional gains (primary hypothesis) at the end of 12 weeks of home- based exercise training and to promote better maintenance of the benefits of pulmonary rehab at 24 weeks than in the no-music group (secondary hypothesis).

C.1.2. General Overview of Design. The proposed study has been designed as a randomized, controlled clinical trial in which COPD patients will be randomized into an exercise program with RAS-enhanced music (RAS- music group) or in an exercise program without music (no-music group). COVID 19 patients will be randomized into an exercise program with RAST-enhanced music (RAST- music group and strength training) or in an exercise program without music (no-music but will have strength training group). Patients will complete testing procedures at pre-randomization, at 6 weeks, immediately post-rehabilitation, and 24 weeks after enrollment. Testing at 6 weeks is included to provide interim follow-up should patients not complete the 12 weeks of training.

C.1.3. Sample Size Calculation.

Sample size was estimated based on a 2-group mixed model design with baseline, 6 and 12-week measurements. Our primary goal is to compare the difference in distance walked during the standard 6MWT over 12 weeks between groups (see **C.1.9.1.a.**). We estimate that the COPD target sample size of 68 patients per group completing 12 weeks will ensure 80% power to detect the differences between treatment arms using a two-sided significance level of 0.05, assuming a correlation of 0.70 between measurements. These estimates are based on our PAD pilot data and include similar standard deviations at baseline and at 6 weeks between groups and over time (232 feet), correlations between measurement of 0.76 to 0.86, and an increase of 87.2 feet at 6 weeks for the RAS- music group, with a slightly higher level for those completing the 12-week assessment. Based on the work of

Table. 2 COPD Study inclusion and exclusion criteria

Inclusion Criteria	Exclusion Criteria
• ≥ 40 yr. of age	• Respiratory infection/COPD exacerbation within the previous four weeks
• FEV ₁ ≤ 70%	• Exercise-limiting heart disease (Congestive heart failure – i.e., New York Heart Association Class III or IV; positive stress test or other indicators of heart disease or complaints of angina during the stress test)
• FEV ₁ /FVC <70%	• Exercise-limiting peripheral arterial disease (stops walking due to intermittent claudication)

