• Mean SpO ₂ ≥ 88% at peak exercise (with or without oxygen supplementation)	• Stops exercise for arthritic pain in knee or hips
• Ability to hear music	• Inability to walk on the treadmill
	• Any unforeseen illness or disability that would preclude exercise testing or training
	• Participation in a formal exercise program within the previous 12-weeks

Liu et al.,¹¹ we estimate no change in the 6MWT in the no-music exercise training group.

COVID 19 sample size was estimated based on a 2-group design with pre- and post-test measurements. Our primary goal is to compare the difference in distance walked during the *standard 6MWT* at 12 weeks between groups. We estimate that over a two-year period we will ensure complete data collection on a total of 72 patients (36 per group). This will ensure a 58% power to detect the differences between treatment arms using a two-sided significance level of 0.05, assuming a correlation of 0.65 between measurements. Our pilot data used to support this estimate include the most conservative correlation observed between measurements ($r=0.65$), and an increase of 41 meters at 12 weeks for the intervention group.

According to the local IRB, enrollment is the equivalent to a patient signing an informed consent. In our three latest studies,^{3,4,94} 30% of patients who signed the informed consent (i.e., enrollees) did not meet pulmonary function criteria or did not qualify for other reasons.⁹⁵ Moreover, based on our previous work, we expect an attrition 12 weeks after randomization of about 8%, and an attrition 24 weeks after randomization of 20%. Accordingly, to have complete data in 136 COPD patients as required by our power calculation (see above), we plan to 'enroll' 243 COPD patients (i.e., signed informed consent) expecting to 'randomize' 170 of them, and to lose 34 of this latter group by week 24 (end of the study). We will enroll 100 patients with COVID 19 into this study.

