Three times a week, patients will complete a muscle resistance/strength training session using professional grade resistance bands with handles (DYNAPRO™). Patients will complete upper, lower, and core body exercises. Training will include 9-11 exercises (e.g., shoulder press, lateral arm raises), will be progressive (i.e., bands with greater resistance will be used as participants' strength increases), and will be completed in two sets of 12-15 repetitions per exercise. Lower body exercises will include calf raises, chair sit to stands, and wall squats or squats with the resistance band. Core exercises will include basic planking exercises and abdominal work. Patients will record that they completed the strength training on their exercise log. We will focus on both upper, lower, and core body strength exercise as patients recovering from COVID 19 have generalized overall body weakness.

Usual Care Group: One week after randomization, patients in the control group will return to the lab to receive educational material on physical activity and general advice based on the 2018, *Physical Activity Guidelines for Americans* 2nd edition (U.S. Department of HHS) (see Appendix 4).¹⁴² Three times a week, patients will complete a muscle resistance/strength training session using professional grade resistance bands with handles (DYNAPRO™) (same as RAS-therapeutic music group).

C.1.7. Promoting & Assessing Adherence to the Exercise Program with and without RAS/RAST-music. To promote and monitor adherence to exercise (with or without RAS-music), all patients will be provided with a 3- axis accelerometer (Fitbit).¹⁰⁰⁻¹⁰² Patients will be instructed to download (sync) data from the Fitbit into their smartphone or iPod devices. These data will be saved in the associated online “Fitbit user account” set up by the study staff. During the 12-week period of exercise training, study staff will call patients on a weekly basis to go over daily and weekly walking data saved in the Fitbit account and to answer any questions that may arise. *To enhance/ensure compliance, our study staff will take a positive approach using motivational interviewing techniques.* After week 12, weekly phone calls will stop. To maintain engagement with study staff, patients will be called again at week 18. At week 23, they will be called to be reminded of the final visit that will take place on week 24.

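### The COVID control arm is described in two incompatible ways, so it is unclear whether COVID controls follow the structured walking programme

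*Combined protocol and SAP*

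**What the plan says.** **Usual-care description.** The introduction, where the COVID cohort is added, sets its main goal as comparing the music exercise programme plus strength training "to 12-weeks usual care and strength training in patients recovering from COVID 19". The COVID exercise section after C.1.6.2 gives the content: "Usual Care Group: One week after randomization, patients in the control group will return to the lab to receive educational material on physical activity". Controls also get general advice based on national activity guidelines (Appendix 4) and the same resistance-band sessions as the music arm. No walking prescription is stated there.

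**Exercise-programme description.** The COVID hypotheses under Objective 1 in A1 begin "Compared to patients randomized to a home-based, exercise program without music (control group". C.1.2 places COVID controls "in an exercise program without music (no-music but will have strength training group". C.1.5 randomizes them to exercise training without music and names strength training as a further component. COVID Objective 4 refers to "responsiveness to rehabilitation achieved with and without concurrent use of RAST music programs". C.1.6.2 sets out a 12-week walking programme for the no-music group, a minimum of 30 minutes on three or more occasions a week, and names direction by RAS/RAST music as the training difference.

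**Related text.** C.1.7 gives every patient a Fitbit and weekly calls about walking data. C.5.3 adds a call after three missed sessions. Neither exempts COVID controls. C.1.3 plans the COVID comparison with 36 per group, 58% power, a two-sided 0.05 level, a correlation of 0.65 and "an increase of 41 meters at 12 weeks for the intervention group". It gives no COVID control-arm change and no COVID SD.

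**The concern.** The endpoint, time point and group sizes of the COVID comparison are stated, but the treatment contrast is not settled. If controls receive advice and bands, the contrast is music plus structured walking against no walking prescription. Any gain in walk distance could come from either component, and the A1 hypothesis, which compares against exercise without music, is not tested. If controls follow the walking programme, the contrast isolates the addition of music.

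The two contrasts support different conclusions and would be expected to differ in size. There is also a delivery risk: staff following C.1.6.2 and staff following the usual-care paragraph could give controls different treatments, and no analysis can undo that.

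**Working it through.** **Can the two descriptions be read as one?**

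- *Exercise without music means only the bands.* C.1.5 rules this out, because it names exercise training and strength training separately. C.1.6.2 defines the no-music programme as walking.
- *Usual care brings in walking by another route.* The Fitbit, weekly calls and missed-session calls may prompt walking, but they are not a prescription. For a control given only advice and bands, it is unclear which sessions would count as missed.
- *The analysis section decides.* It does not. H1A in C.2.1 is worded for COPD patients only.
- *The objectives decide.* COVID Objective 3 asks "whether there is any change in 6-minute walk distance and perceived functional improvements in the control group", which leaves the expected control response open.

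**Does the power statement reveal which control was planned for?**

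The 58% cannot be reproduced directly, because C.1.3 omits the COVID SD and control change. It can be solved backwards. This is an illustration only.

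1. Two-sample t-test, n = 36 per group, two-sided 0.05, df = 70, noncentrality d × √(36/2). Power of 0.58 requires d = 0.5166.
2. Assume the control change is zero, so the difference is 41 m. The analysis SD is 41 / 0.5166 = 79.4 m.
3. Convert to a raw SD with r = 0.65:
   - change score: √(2 × (1 − 0.65)) = 0.837, so 79.4 / 0.837 = 94.9 m
   - baseline-adjusted: √(1 − 0.65²) = 0.760, so 79.4 / 0.760 = 104.4 m
4. Assume instead the only planning SD in C.1.3, taken from the peripheral artery disease pilot for the COPD calculation: "similar standard deviations at baseline and at 6 weeks between groups and over time (232 feet". That is 232 × 0.3048 = 70.7 m. The difference giving 58% is then:
   - change score: 0.5166 × 70.7 × 0.837 = 30.6 m, a control gain of 41 − 30.6 = 10.4 m
   - baseline-adjusted: 0.5166 × 70.7 × 0.760 = 27.8 m, a control gain of 41 − 27.8 = 13.2 m
   - unadjusted 12-week values: 0.5166 × 70.7 = 36.5 m, a control gain of about 4.5 m
5. With SD 70.7 m and zero control gain, power would be 0.83 (change score) or 0.89 (baseline-adjusted), not 0.58.

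The text therefore fits a control arm that does not improve with a larger SD, or one that improves modestly with the borrowed SD.

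**How much could the choice of control matter?** Suppose the 58% was computed for a 41 m difference and controls in fact improve by walking. By the normal approximation, the standardized effect at 58% is 1.960 + 0.202 = 2.162. If the arms differ by 75%, 50% or 25% of 41 m (30.75, 20.5 or 10.25 m), power at 36 per group is Φ(2.162 × fraction − 1.960), or about 37%, 19% or 8%. The fractions are assumptions; the documents give no expected change for COVID controls.

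**Minor COPD point.** C.1.6.2 names music direction as the training difference and says all other methods match. The described cycles do not. C.1.6.1.c gives about 4, 4 and 2 minutes of slow, fast and slow walking; C.1.6.2 gives about 2, 4 and 1. The fast share is 4/10 = 40% with music against 4/7 = 57% without. If the first two music phases total 4 minutes, it is 2/6 = 33%.

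**The case against.** The strongest reply is that the plan leans towards usual care. The usual-care paragraph is the only operational text written specifically for COVID controls, it matches the stated main goal, and COVID Objective 3 adds a question about control change that the COPD version lacks. The exercise-without-music wording could be carried over from the COPD text. That is plausible, but it leaves the contradiction in the hypotheses, design overview and randomization text.

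Some supporting text is weak, and this is accepted. RAST in C.1.6.2 does not prove that section covers COVID patients, since A.3.1.2 uses the same label under a COPD heading. The with-and-without-music wording in Objective 4 and the C.1.7 title fits either version, because both arms do strength training. The parenthesis in C.1.2 could be a gloss rather than an extra component. The statement under potential benefits that there is no non-exercising control group settles nothing, because band training is exercise. Without all of these, A1 and C.1.5 still conflict with the introduction and the usual-care paragraph.

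Appendix 4 and the operations manual cited in C.1.12 are not visible and may define actual delivery, so nothing is inferred from their absence. The power back-calculation does not show which control was meant or that 58% is wrong. The COPD fast shares rest on approximate durations and ignore the tempo step-ups, so they do not compare training dose.

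**Conclusion.** The concern holds for the COVID cohort. Its control arm has two incompatible descriptions, and the choice changes what the COVID primary comparison tests: music added to walking, or a walking-plus-music package against advice, with strength training in both arms. Followed as written, the usual-care paragraph leaves the A1 hypothesis untested.

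The contrast in prescribed walking is either equal in minimum length and frequency or a prescription against none stated. The real gap under usual care is unknown, because the monitoring and calls may narrow it. The 58% is not shown to be wrong, but a reader cannot tell which control it was computed for; the SDs and control gains above rest on the stated assumptions. The COPD primary analysis is not affected by this contradiction. The COPD cycle mismatch is a small reconciliation with unknown direction of bias.

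**What to change.** - Reconcile the introduction and the usual-care paragraph with A1, C.1.2, C.1.5 and C.1.6.2 so that one COVID control is described throughout. Which one is for the investigators to decide; no prescription is proposed here.
- Make the COVID hypotheses and permitted conclusion match. If controls receive no structured walking programme, the conclusion concerns the package, not the music.
- State in C.1.7 and C.5.3 whether the weekly and missed-session calls apply to COVID controls.
- Give in C.1.3 the control-arm change and SD behind the 58% for the chosen control.
- For COPD, reconcile the cycle descriptions in C.1.6.1.c and C.1.6.2, or say in C.1.6.2 that phase lengths also differ.

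The cost is wording in the protocol and analysis plan, including one sentence on the power inputs. No patients, visits or measures are added. The COVID conclusion may have to be narrower.

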C.1.9.5. Questionnaires: Self-reported physical function and quality of life will be evaluated using eight questionnaires (see **C.1.9.5.a. to C.1.9.5.e.**).

C.1.9.5.a. Chronic Respiratory Disease Questionnaire (CRQ). This questionnaire is designed to determine how the lives of patients with chronic airflow limitation are affected by the illness and the perceived impact of symptoms and limitations on quality of life.¹¹² Test-retest reliability and validity of the CRQ are well established.¹¹² Patients will not be informed of their previous responses on the questionnaire when the CRQ is administered at week 6 and 12 and 24. CRQ scores will be used as covariates in the final analysis if appropriate (see **C.2 Statistical Analysis**).

C.1.9.5.b. Short Form-36 Health Survey (SF-36): This is a general health-related quality of life

instrument to quantify perceived physical function and mental health.⁸ The SF-36 will be used to describe the sample and to have a comparator measure to published clinical pulmonary rehabilitation programs.¹¹³

C.1.9.5.c. Charlson Comorbidity Index. This validated¹¹⁴ and widely utilized index^{80,82} will be used to determine whether comorbidities influence study outcomes (see **C.2 Statistical Analysis**).

C.1.9.5.d. Depression and Anxiety. To control for the influence of ongoing depression and anxiety on adherence, the Center for Epidemiologic Studies Depression Scale (CES-D)¹¹⁵ and the State-Trait Anxiety Inventory (STAI)¹¹⁶ will be administered at baseline and at major data collection time-periods. CES-D and STAI scores will be used as covariates in the final analysis as appropriate.

C.1.9.5.e. Self-Efficacy. The Self-Efficacy for Walking¹¹⁷ and the Self-Efficacy for Shortness of Breath questionnaires¹¹⁸ will be used to measure self-efficacy at all time periods.¹¹⁷ These are reliable and valid¹¹⁸ instruments designed to assess a patient's confidence in keeping shortness of breath from interfering from walking or from doing what they want to do.

C.1.9.5.f. COPD Assessment Test The COPD Assessment Test (CAT) measures the impact COPD has on patient's well-being and daily life.

C.1.9.5.g Coronavirus Anxiety Scale (CAS) Assesses dysfunctional anxiety associated with the COVID19

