H1A: IN PATIENTS WITH COPD, IMPROVEMENTS IN 6-MINUTE WALKING DISTANCE WILL BE GREATER AFTER COMPLETING 12 WEEKS OF A HOME-BASED, EXERCISE PROGRAM WITH RAS-ENHANCED MUSIC THAN AFTER A HOME-BASED, EXERCISE PROGRAM WITHOUT MUSIC.

The analysis of the primary outcome (improvements in 6-minute walking distance) is based on all data collected during the intervention period—baseline, 6 and 12-weeks. We will use a mixed-model analysis that includes treatment, time and treatment-by-time interaction terms. Specifically, we will test whether the treatment- by-time interaction differs from 0. This model will automatically account for missing data

where missing at random is assumed. We will conduct a sensitivity analysis^{129,130} based on the results of the mixed model analysis to determine whether other assumptions regarding the missing data may produce different results. One component of the sensitivity analysis will also include adjustment for

baseline demographic and health covariates.

C.2.2. Statistical Analysis: Secondary Hypotheses

Statistical analysis for H_{1c} will parallel that of H_{1a} .

H_{1D} : THE RAS-ENHANCED MUSIC GROUP WILL DEMONSTRATE GREATER INCREASES IN HEALTH-RELATED QUALITY OF LIFE (QOL) THAN THE CONTROL GROUP.

Statistical analysis for H_{1d} will parallel that of H_{1a} .

H_2 : THE RAS-ENHANCED MUSIC GROUP WILL ACCUMULATE A GREATER VOLUME OF DAILY PHYSICAL ACTIVITY THAN THE CONTROL GROUP. THIS WILL BE DEMONSTRATED BY GREATER PHYSICAL ACTIVITY AT 12 WEEKS (ACTIGRAPHY).

Statistical analysis for H_2 will parallel that of H_{1a} .

H_3 : THE RAS-ENHANCED MUSIC GROUP WILL MAINTAIN IMPROVEMENTS IN MEASURED AND PERCEIVED FUNCTION AT 24 WEEKS TO A GREATER EXTENT THAN THE NO-MUSIC CONTROL GROUP.

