In the statistical analysis of H_3 , we will use independent t-tests to compare the changes in measured function (distance walked in the 6MWT and perceived function (questionnaires) between 12 and 24-weeks between the RAS-music and the no-music groups. We will also conduct paired t-tests within each group to determine whether values at 24 weeks are worse than those at 12 weeks. These computations will be based on those patients with 12 and 24-week data. To assess whether patients included in the H_3 analysis are representative of the original randomized groups, we will also compare demographic and health measures (i.e., FEV₁ percent predicted, comorbidities, depressive symptoms and exacerbations) of patients included in the H_3 analysis to patients who were not.

C.2.3. Statistical Analysis: Exploratory objective: [exploratory objective not reported]

TO ASSESS IMPACT OF PHYSIOLOGICAL AND PSYCHOLOGICAL PHENOTYPE AND CLINICAL FACTORS ON RESPONSIVENESS TO REHABILITATION ACHIEVED WITH AND WITHOUT CONCURRENT USE OF RAS-MUSIC. PHYSIOLOGICAL FACTORS INCLUDE: SYSTEMIC INFLAMMATION (HS-CRP), QUADRICEPS STRENGTH, RECRUITMENT AND FATIGUE, QUADRICEPS FUNCTION AND DIMENSION AFTER REHABILITATION. PSYCHOLOGICAL FACTORS INCLUDE: SELF-EFFICACY, ANXIETY AND DEPRESSION. CLINICAL FACTORS INCLUDE: ADHERENCE TO THE 12-WEEK PROGRAM, ADHERENCE TO FOLLOW-UP AND NUMBER AND SEVERITY OF EXACERBATIONS.

To assess the impact of the above confounders two separate analyses will be conducted: (a) A linear regression model with changes from baseline to 12 weeks of training as the dependent variable, and assigned treatment group, physiologic and psychologic phenotype and clinical factors as the independent variables, and

(b) A mixed model ANOVA with baseline, and 12 and 24 weeks measurements as dependent measures and assigned group, physiologic and psychologic phenotype and clinical factors as the independent variables.

C.3. Expected Outcome: We expect to demonstrate that improvements in 6-minute walking distance from baseline to 12 weeks will be greater after completing 12 weeks of a home-based, exercise program with RAS- music than after a home-based, exercise program without music.

C.4. Alternative Outcomes. Our primary hypothesis will be rejected if, at 12 weeks, improvements in 6-minute walking distance are not greater with exercise-training plus RAS-music than with exercise-training without music. In this case, at least three alternative outcomes will be considered.

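### The primary COPD model uses baseline 6MWT only as an unconstrained response, which is valid but gives up precision; C.2.1 also leaves open whether the interaction test has 1 or 2 degrees of freedom.

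*Combined protocol and SAP*

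**What the plan says.** C.2.1 bases the primary COPD analysis on the baseline, week-6 and week-12 walks: "We will use a mixed-model analysis that includes treatment, time and treatment-by-time interaction terms". The test is then given as: "Specifically, we will test whether the treatment- by-time interaction differs from 0". The section does not state how time is coded, the degrees of freedom, the covariance structure or a contrast at a named visit. The only adjustment it mentions is one component of the sensitivity analysis, for "baseline demographic and health covariates".

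Other sections allow further covariates, among them: "CRQ scores will be used as covariates in the final analysis if appropriate" (C.1.9.5.a) and "CES-D and STAI scores will be used as covariates in the final analysis as appropriate" (C.1.9.5.d). None is baseline 6MWT. C.1.5 and C.1.9.1 call for two standard walks at baseline without saying which walk, or what summary, is the baseline value.

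The hypothesis itself concerns 12 weeks. H1a in C.2.1 is worded that way. C.3 says: "We expect to demonstrate that improvements in 6-minute walking distance from baseline to 12 weeks will be greater". C.4 says: "Our primary hypothesis will be rejected if, at 12 weeks, improvements in 6-minute walking distance are not greater". C.2.2 carries the H1a method over to H2, which is also a 12-week claim.

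**The concern.** **Precision.** With baseline as one of three responses and separate arm means at every visit, the comparison of interest is a difference in change scores. In a randomized trial the true baseline means are equal. A model that uses this fact, by constraining those means or by conditioning on baseline, estimates the same week-12 effect with smaller variance. The data are already collected, so the loss is avoidable.

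**Which test.** With three visits, the interaction is a 1-df slope difference if time is linear and a 2-df joint test if time is categorical. The 2-df test does not isolate week 12, whereas the study's conclusion is framed at week 12. Until the coding is fixed, the primary p-value depends on a choice that can still be made after the data are seen.

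**Working it through.** **Inputs (C.1.3).** SD 232 ft; planning correlation r = 0.70; pilot correlations 0.76 to 0.86; gain 87.2 ft at week 6, described as slightly higher at week 12; no change in controls; 68 completers per group; 80% power; two-sided 0.05. *Assumption:* the effect at week 12 is 87.2 ft.

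**1. Reproduce the plan's figure.** SD of the baseline-to-week-12 change = 232 × √(2(1 − r)). At r = 0.70 this is 232 × √0.60 = 179.7 ft. With the noncentral t distribution, 87.2 ft needs 68 per group for 80% power, and power at 68 is 80.2%. The plan's 68 is therefore the size for a 1-df unadjusted change contrast.

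**2. Adjust for baseline.** SD = 232 × √(1 − r²). At r = 0.70 this is 232 × √0.51 = 165.7 ft. The variance ratio, adjusted to unadjusted, is (1 − r²) / (2(1 − r)) = (1 + r)/2, that is 0.85, 0.88 and 0.93.

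| r | SD change / adjusted (ft) | Power at 68 per group, change / adjusted | N per group for 80%, change / adjusted |
|---|---|---|---|
| 0.70 | 179.7 / 165.7 | 80.2% / 86.1% | 68 / 58 |
| 0.76 | 160.7 / 150.8 | 88.1% / 91.7% | 55 / 48 |
| 0.86 | 122.8 / 118.4 | 98.4% / 98.9% | 33 / 30 |

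**3. What a linear-time interaction tests.** With complete data at three equally spaced visits, the slope weights the visits −1, 0, +1. That is the same baseline-to-week-12 change contrast as in step 1.

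**4. What a 2-df interaction tests.** *Assumption:* equal correlations of 0.70 between all pairs of visits. Each change has variance 0.60 × 232² = 32,294, and the covariance of the two changes is half that, a = 16,147. For arm differences d₆ and d₁₂ in change at weeks 6 and 12, the noncentrality is (68/2) × 2(d₆² − d₆d₁₂ + d₁₂²)/(3a).

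- (87.2, 87.2) ft: 34 × 2 × 7,603.84 / 48,442 = 10.67, power 83.2%.
- (87.2, 0) ft: the bracket is again 87.2², so noncentrality is 10.67 and power 83.2%.

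The 2-df test rejects equally often for a lasting effect and for one that has vanished by week 12. The second pattern is only an illustration; C.1.3 does not expect it.

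**5. Cost of naming week 12, like for like.** Effect (87.2, 87.2) ft, r = 0.70, 68 per group. *Assumption* for decaying correlation: √0.70 = 0.837 between adjacent visits and 0.70 from baseline to week 12.

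| Correlation | Baseline handling | Week-12, 1 df | 2 df | Difference (points) |
|---|---|---|---|---|
| Equal | unadjusted | 80.2% | 83.2% | −3.0 |
| Equal | adjusted | 86.1% | 90.9% | −4.8 |
| Decaying | unadjusted | 80.2% | 93.6% | −13.4 |
| Decaying | adjusted | 86.1% | 95.7% | −9.6 |

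**The case against.** The strongest reply is that nothing here is broken. The interaction already compares change from baseline, the sample size reproduces without adjustment, and the gain is small where the correlation is high: 3.6 points at r = 0.76 and 0.5 at r = 0.86. If 85 per group are randomized and 8% miss week 12, with equal correlations, power goes from 86.2 to 90.9%, 92.6 to 95.2% and 99.4 to 99.6%, gains of 4.7, 2.6 and 0.2 points. All of this stands. Adjustment is an inexpensive improvement to a valid analysis.

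On the choice of test, the reply is that week 12 is already signalled: H1a says so inside C.2.1, the sample size fits the 1-df change contrast, and linear time yields that contrast when visits are complete. This stands in large part and is why the point is secondary. It does not remove the gap, because C.2.1 never says which test is meant. C.2.3(a) does regress the 12-week change on treatment, but it is exploratory and includes post-randomization factors, so it cannot serve as the primary test.

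Three stronger readings are tempting and unsupported. A reader might infer that the primary analysis ignores baseline 6MWT or is biased by chance imbalance; it does not ignore it, since baseline is a response, and the randomized comparison of change is unbiased. A reader might infer that the 80% power claim fails; step 1 reproduces it. A reader might infer that naming week 12 gains power; step 5 shows the opposite when the effect is full by week 6 and persists.

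**Conclusion.** The point holds as a matter of precision, with a smaller one of pre-specification. Leaving the baseline arm means free costs 5.9 power points at the planning correlation (80.2 against 86.1%), equivalent to 10 patients per group (68 against 58), and less at the pilot correlations. This rests on a common SD of 232 ft and on 87.2 ft at week 12. C.1.3 gives that effect only for week 6, and a somewhat larger week-12 effect would raise both power figures.

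The unspecified degrees of freedom matter only if time is categorical and the joint test is used. The reason to name week 12 is that the test should answer the question posed in H1a, C.3 and C.4. The power differences in step 5 depend on the assumed correlation pattern and effect path. Nothing here applies to the COVID-19 cohort, which has its own sample size calculation.

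**What to change.** State in C.2.1 that the primary COPD test is the 1-df, two-sided 0.05 between-arm difference in standard 6MWT at week 12, from a mixed model with categorical time and unstructured covariance. Bring in baseline 6MWT in one of two ways, chosen in advance: as a covariate, with weeks 6 and 12 as the responses; or as a response with baseline means constrained equal across arms. State which of the two baseline walks, or which summary of them, is the baseline value. Report week 6 as secondary. Say which contrast H2 uses, since it inherits the method.

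The cost is SAP wording; no new data are needed and the sample size does not change. There are two downsides. An effect seen only at week 6 would no longer count as primary success. And compared with a 2-df test, when the full effect is present by week 6 and persists at r = 0.70, naming week 12 costs about 3 points (both unadjusted) or 5 (both adjusted) under equal correlations, and about 13 or 10 if correlation decays. Baseline adjustment offsets part of this by adding 5.9 points to the week-12 test, although a 2-df test would also gain from it (83.2 to 90.9% under equal correlations).
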